 - *Day 10:* Participant will visit the study center briefly to pick-up meals that will be consumed on Days 11-14. Participant will return all uneaten foods and containers to the study team to determine actual food consumption during the preceding period. A stool collection kit will also be provided.
 - *Day 14:* Participant will visit the study center in the fasting state. The participant will provide a fecal sample that was self-collected during the preceding 24-hours. A urine sample will be collected to assess compliance to test meals. Participant will also return all uneaten foods and containers to the study team to determine actual food consumption during the preceding period. Anthropometrics and blood pressure will be assessed. Blood will be collected (0 min) and then an oral glucose tolerance test (75 g) and gut permeability test as described.⁵⁹ will be completed simultaneously. After emptying their bladder, the participant will ingest a 75 g glucose solution containing non-digestible sugars. Blood samples will be collected at 30-min intervals for 3-hours. Participant will be provided urine collection containers to self-collect urine for the subsequent 24-hours. During this 24-hour period, participants will also be provided controlled meals and beverages.
 - *Day 15:* Participant will return to the study center to provide collected urine. All procedures for Trial 1 are deemed complete.
- **Wash-out Period.**

Trial 1 and Trial 2 will be separated by at least two-weeks for men. However, the washout period for women may be extended to enable testing during the same phase (\pm 3 days) of the menstrual cycle.

- **Trial 2 Procedures (2-week intervention to WWB or WB).**

All procedures for Trial 2 will be identical to those of Trial 1 with the exception that the participant will receive the alternative test meals. If the participant was assigned WWB in Trial 1, WB will be assigned in Trial 2. If WB was assigned in Trial 1, then WWB will be provided in Trial 2.

- **Study Completion**

On Day 16 of Trial 2, the participant's involvement in the entire study is completed. A check will be provided to the participant in accordance with the payment schedule (up to \$350) that is outlined in the consent form.

4. *Blood Collection and Sampling Handling.* Once at baseline (day 0; 14 mL), and at each time point of the postprandial trial (20 mL * 7 timepoints over 3-h), a blood sample will be collected into evacuated blood collection tubes. Collecting a total of 154 mL or 0.65 cups once during each study arm is necessary to ensure an adequate volume of plasma and serum for each time point to accurately analyze levels of glucose, insulin, endotoxin, and pro-inflammatory genes. During blood collection, participants may feel an initial pain when inserting the needle, bruising around the insertion area, lightheadedness, or fainting, which are common when donating blood. However, we do not foresee any additional significant risks for collecting this amount of blood over 3 hours, other than the risks stated previously.

Throughout the span of the study (~8-12 weeks in duration depending on participant/investigator availability) which consists of four weeks total of controlled feeding, a blood collection at day 0 and 14 and then repeated following a \geq 2-week washout period, and 1 screening day, we will be collecting a total of ~318 mL or ~1.34 cups) of blood. Urine will be collected in provided containers (VWR) containing 10% thymol to inhibit bacterial growth. We will then have the participants return their urine samples to the study center or coordinate with study personnel to meet at a public and mutual location to return their samples within 24-h after collection. Feces will be collected using a commercial commode specimen collection system (Fisher Scientific). Briefly, the collection kit consists of the necessary materials (e.g., gloves, waste bag) for participants to easily and hygienically collect their stool without contaminating the sample or themselves. Volumes of urine will be recorded and fecal mass and observations will be recorded based on the Bristol Stool Chart.⁸⁸

During each blood collection, plasma will be obtained by centrifugation and then transferred to cryogenic storage tubes. Serum samples will be obtained by allowing the blood to clot, followed by centrifugation and transfer to cryogenic storage tubes. Tubes will be stored at -80° C until analysis can be completed. Analyses will include plasma glucose, insulin, triglyceride, HDL cholesterol, proinflammatory genes and/or proteins (e.g., TLR4, CD14, MD2, MyD88, p65, IL-1, IL-6, IL-8, TNF- α , MCP-1), and serum endotoxin. Urine will be stored at -80°C until analysis can be completed. Analysis from urine will include sucralose, erythritol, lactulose, and mannitol. Fecal samples will be stored at -80°C until analysis can be completed. Feces analysis will include microbiota composition, calprotectin, myeloperoxidase (MPO), and fecal metabolomics analysis. Remaining plasma, serum, urine, and fecal samples not used for these analyses will be archived for 5 years at -80 C in the event we decide to measure additional biomarkers. Appropriate notation has been made in the informed consent to alert participants that we will be archiving specimens and that they have the right to refuse our use of these specimens for future analyses. Lastly, approval from OSU IRB will be sought via a protocol amendment prior to the analysis of any additional biomarkers not specified herein.

E. Privacy/Confidentiality

For all data and records that are a part of this study, a number (i.e. code) will be assigned to each participant and will only be available to research personnel. Any records containing the names of participants will be stored in a locked filing cabinet or on a password protected computer in the PI's laboratory or office.

Research personnel under the supervision of the PI and the PI himself will be the only individuals that have access to this information. The names of participants will not be used for publication in any form. The records will be maintained until the data are published, up to a maximum of five years. All archived samples will be coded, but the key linking the code to each participant's identifiable information will have been destroyed. In addition, participants will be instructed that their participation in this study is voluntary and that they may withdraw at any time without prejudice. Data (biochemical values) obtained from this study will be stored on a computer in the PI's laboratory. In addition, a backup of digital data will be stored on the PI's computer in his office. Both computers are password protected and both doors are locked when work areas are not in use.

F. Internal Validity

For all data and records that are a part of this study, a number (i.e. code) will be assigned to each participant. This will minimize measurement bias when performing analysis on dietary records, and biochemical markers because all samples/records will be coded. The codes will only be broken once data analysis has been completed and verified by the PI.

G. Medical Safety Plan

All aspects of the clinical study will be conducted in [name] clinical lab located in [name]. Participants will be fasted for 10-12 hours prior to each study visit. We recognize that certain risks associated with fasting include: hypoglycemia, weakness, and fainting. This duration of fasting is consistent with guidelines set forth by the American Diabetes Association to minimize risk to the individual⁶² when determining fasting blood glucose concentrations.

Risks related to hypoglycemia are anticipated to be low due to participants' already marginally elevated fasting blood glucose (study entry criteria = 100-126 mg/dL). They will also be ingesting a glucose beverage containing 75 g of glucose immediately following the fasting period. Throughout each visit to the study center, participants will be closely monitored by a member of the study team (PI, postdoctoral scholar, or graduate student). They will monitor the safety and well-being of participants for any signs and symptoms of hypoglycemia including: confusion, dizziness, irritability, weakness, headaches, and fainting. Additionally, [name] (PI; [name]) has an academic office in close proximity to the study center and has significant experience coordinating clinical research studies involving overnight fasting, and other dietary- and carbohydrate-challenges, thereby supporting the competency of our research team in managing potential adverse events relating to fasting glucose and glycemic responses.

Consistent with our prior studies of similar design, and to ensure participant safety, all blood collection procedures throughout each study visit will occur while positioned on a hospital bed in the prone position or while seated in a phlebotomy chair. In the event that a participant was to become weak, dizzy, or faint, they would already be in a safe position to minimize risks associated with these symptoms. In the event that hypoglycemia-related symptoms occur, the study would be terminated to allow the participant to recover. We are prepared to provide pre-packaged beverages and snacks containing simple carbohydrates (e.g. Gatorade, fruit juice, apple sauce, crackers) that will allow for rapid restoration of blood glucose. These food items will be stored in a refrigerator, located in the adjacent metabolic research kitchen, that is dedicated for foods used in research studies. Participant status (e.g. attentiveness, skin color) will be monitored in our clinical laboratory to ensure recovery. The clinical area where participants undergo blood draws is also equipped with first-aid measures (e.g. smelling salt) and all study team members are trained to assist with basic first-aid application if needed.

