**Assessing Gut Microbiota Mediated Health Outcomes of Whole Wheat and Its Major Bioactive Components
Study Protocol
NCT Number: NCT05318183
Date: 11/21/2021**

Assessing gut microbiota mediated health outcomes of whole wheat and its major bioactive components

I. Objectives

The use of functional foods or their bioactive components to manage chronic disorders has become popular in recent years. One dietary product that can be tapped for its health benefits is whole grain. Observational studies suggest an inverse relationship between the intake of whole grain and obesity, prediabetes, some cancers, and all-cause mortality. A growing body of clinical evidence (mostly small randomized clinical trials) demonstrates positive effects of whole grain on certain risk factors for chronic diseases and cardiometabolic abnormalities; however, outcomes of clinical interventions have revealed substantial interpersonal variation in the health benefits, with a subset of individuals not exhibiting any measurable benefits. Whole grains/whole wheat contains significant amounts of bioactive phytochemicals in addition to its well-recognized fiber content. Outcomes of many studies support that whole grains/whole wheat provide favorably improve human health by the direct effects of these phytochemicals and/or their microbial metabolites. Thus, the objectives of this study are to investigate the gut microbiota-mediated effect of whole wheat consumption, the most widely consumed whole grain, on the fecal and plasma metabolomes, metabolic health, and gut health in a cohort of adults with prediabetes. We hypothesize that gut microbial metabolism of whole wheat and its major bioactive components is a determining factor of human health benefits; and by understanding the gut microbiome--mediated benefits of whole grain, we can truly harness its benefits for metabolic health in humans.

II. Background and Rationale

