
C. Gut microbial diversity may explain the personalized protective effects of whole wheat against prediabetes. As evident by the sharp incline in the prevalence of prediabetes, blood glucose levels are rapidly increasing in the worldwide population. It is estimated that impaired glucose tolerance will affect at least 37% of the adult population in the US alone.²⁷ Prediabetes, characterized by chronically impaired blood glucose responses, is a significant risk factor for type II diabetes mellitus (T2DM), with up to 70% of prediabetics eventually developing the disease.²⁸ It is also linked to other manifestations, collectively termed metabolic syndrome, including obesity, hypertension, non-alcoholic fatty liver disease, hypertriglyceridemia, and cardiovascular disease.²⁹ Thus, maintaining normal blood glucose levels is considered critical for preventing and controlling metabolic syndrome.

D. Summary. This overview demonstrates that consumption of whole grain foods has been associated with decreased risk of obesity, prediabetes, and type 2 diabetes.^{1, 30-32} However, mechanisms mediating the protective effect of whole grains are unclear, although glycemic response and insulin sensitivity are the most common mechanisms suggested by epidemiological studies.³³⁻³⁶ An early report has raised the possibility of gut microbiome-mediated effects linking cereal fiber consumption with decreased risk of T2DM;³⁷ this knowledge gap continues to persist. It was suggested that modifications in gut microbiota, gut fermentation, and influences of yet unknown molecular factors such as phytochemicals may affect insulin sensitivity and further development of type 2 diabetes. Recent results suggest a link between changed gut microbiota and varied glycemic responses.^{1, 13, 14} Furthermore, subjects with T2DM had depleted *Bifidobacteria*,³⁸ and also the level of glucose tolerance was associated with certain gut bacteria.³⁹ Another review concluded that despite convincing epidemiological evidence, *the lack of controlled clinical studies to support or explain the mechanisms underlying the protective effect of whole grains against type 2 diabetes.*⁴⁰ Thus, this application **aims to uncover** the role of gut microbiota and their metabolites of whole wheat bread (WWB) components in mediating blood glucose excursions in prediabetes. We will

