Based on prior studies,¹³ we expect a >25% within-trial decrease in postprandial blood glucose by WWB in high-responders compared to WB. While a statistically significant between-treatment effect is also expected, our study is designed to define ‘high-responders’ vs ‘low-responders’ towards precision nutrition rather than achieve group mean differences by bread treatment.¹⁴ In addition, we expect reduced serum endotoxin during WWB intervention, as metabolic endotoxemia is known to initiate insulin resistance in obese persons.^{41, 42} These benefits are expected to occur through an anti-inflammatory mechanism that attenuates gut-derived endotoxin translocation⁴³ or an antimicrobial activity of WWB that depletes pyrogenic Gram-negative bacteria. In support of the former, we expect WWB will decrease small intestinal and colonic permeability,⁴⁴ based on decreased urinary excretion of lactulose/mannitol and sucralose/erythritol. WWB may also alter, at least in a subset of the study participants, the gut microbial composition, as reported previously in both healthy adults as well as in persons with MetS (e.g. an increase of *Lachnospira*, *Faecalibacterium*, *Prausnitzii*, and *Prevotella copri* abundance and a decrease in *Enterobacteriaceae* abundance in the WWB group^{45, 46}). It is also possible to detect selective antimicrobial activities of WWB (possibly due to its rich phytochemicals)^{16, 47} and consequentially decreased LPS-producing Gram-negative bacteria. If these findings are consistent in a subset group of study participants who have larger changes of glycemic response post WWB intervention, they will collectively suggest a mechanism, at least in part, that the multi-facet health benefit of WWB consumption is gut microbiome-dependent. Meanwhile, with our combined targeted and untargeted metabolomics approaches, we expect a group of known (e.g., energy metabolism metabolites and amino acids)^{48, 49}, and unknown metabolic features may change significantly in fecal and blood metabolome between WWB and WB intervention. Taken together, these studies will establish a solid foundation for determining health and metabolic effects on the human host based on the composition and microbial metabolic capability of gut microbes.

IV. Pitfalls and Alternatives

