2. Recruitment. We will recruit participants through posted flyers, e-mail, electronic and newsprint advertisements (e.g. campus student and faculty/staff newspapers, local and regional newspapers; see attachment “*Advertisements*”), and word of mouth. The posted advertisements will instruct interested participants to call the study center ([name] Laboratory, Department of Human Sciences) or complete an online pre-screening survey to obtain further information. During the phone-in hours, a trained individual (i.e. project coordinator or graduate assistant) will be available to describe the study and determine preliminary qualification by conducting a scripted phone interview (e.g. do you take dietary supplements?, do you smoke?; see “*Phone Script*” attachment). The individual will record answers and assess whether the person calling is likely or not to be an acceptable study participant. If the caller and the interviewer agree that the caller should participate, the prospective participant will be invited to a screening meeting, where the study will be fully described, and the individual will be provided a consent form to complete prior to any involvement in the study procedures. Data collected during this phase will include participant’s age, health status, physical activity, and contact information (see “*Informed Consent*” attachment).

3. Power Calculation and Data Analysis. [name] (biostatistician; *co-PI and Dept of Biomedical Informatics*) performed a power analysis. To ensure that the order by which each participant completes each trial is randomized, a random sequence generator (<http://www.random.org/sequences/>) will be used to determine the order by which each participant will undergo the two trials. We will primarily compare the

within-subject changes (WWB endpoint vs. WB endpoint) between high-responders and low-responders. We anticipate to have 6-12 high-responders and 5-10 low-responders of the total 40 study participants to achieve 80% power to detect a 1.6-fold difference in the changes of postprandial glucose levels (AUC from 0 to 180 minutes) between high-responders and low-responders, at the expected coefficient of variation (CV) 0.5 at a significant level of 0.05.

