Mixed effect modeling will be performed, diet and time will be included as fixed factors while participant serves as a random factor. False discovery rate (FDR) will be used to control type I error rate for microbiome and metabolome data, while the Bonferroni method will be applied for other measures (e.g., inflammatory markers). Data will be first normalized before analysis. Spearman correlations will be calculated to define associations between microbes, inflammatory genes, metabolites that show significant changes in highresponders.

To test whether the changes in microbes after WWB intake associate with the biological response, logistic regression will be fitted to each of the potential microbes or as a combination. We will also couple the logistic regression with receiver-operating characteristic (ROC) analysis to evaluate the specificity and sensitivity of the microbes that predict participants' biological response, and the area under the curve (AUC) of the microbial model will be displayed. Data analysis will be performed in R (open resource) or SAS (SAS, Inc; Cary, NC). The sample size was calculated in PASS 20 (NCSS, LLC; Kaysville, Utah).

C. Measurement/Instrumentation

All procedures will take place in the Human Nutrition Program located in Evans Laboratory. Infrastructure that is present includes a metabolic research kitchen, a private office to meet with participants, a clinical research laboratory for performing phlebotomy and research procedures, and a separate biochemical laboratory for processing and preserving biological specimens.

1. *Anthropometric Parameters and Blood Pressure.* At screening, day 1, 7, and 14, participants will rest for 15 minutes prior to determining blood pressure using an automated blood pressure cuff. BMI will be calculated from height determined from a wall-mounted stadiometer and weight from a calibrated scale.

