2-1/4" (14.6 × 8.3 × 5.7 cm) loaf pan and fermented for 52 min at 30 °C and 85 % relative humidity, then proofed for 25 min, again for 33 min and punched between proofs. Finally, the dough will be baked at 215 °C (Doyon convection oven, Menominee, MI) for 17 min. The bread in this study will be made with limited ingredients to focus on the influence of endogenous chemistry in whole wheat flour on health activity of whole wheat bread.

5. *Dietary Control.* To improve diet homogeneity and limit potential confounding effects of whole grain/wheat intakes on study outcomes, participants' basal diets will be rigorously controlled during each 2-wk intervention by a registered dietitian ([name]) to provide 50-60% energy from carbohydrate, 25-35% fat, and 15-25% protein consistent with the typical American dietary pattern. Participants will be required to consume bread-containing test meals at breakfast and lunch each day; these will be consumed at the study center 4 d/wk during each 2-wk study arm to establish rapport and ensure compliance to study procedures. The WB and WBB used in this study will be prepared in the pilot lab in the Department of Food Science and Technology under the auspice of [name] (co-investigator of the project) to ensure compositional consistency.

Participants' basal diets, including bread-containing test meals, will be administered in a eucaloric manner by estimating energy requirements using the Harris-Benedict equation,⁵⁸ with appropriate adjustment for physical activity.⁴⁵ During each 2-wk study arm, participants will return any uneaten foods, which will be weighed to determine actual energy and nutrient intakes using NDSR dietary analysis software. All foods and beverages will be identical between study arms with the exception of WBB and WB. Participants will also complete a food diary to record the consumption of any non-prescribed foods. Non-fasting body weight will be measured 3 times/week throughout the study to monitor weight stability. If body mass fluctuates >1 kg, the participant's prescribed energy intake will be adjusted to prevent additional weight loss or gain. Thus, our approach will minimize participant burden while applying sufficient dietary rigor to test the hypothesis that WBB consumption, principally through its bioactive phytochemicals, improves glucose tolerance in a microbiota-mediated manner.

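### The objective is worded as microbiota mediation, but the plan estimates no indirect effect; a positive result would support association or microbiome-dependent response, not mediation

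*Combined protocol and SAP*

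**What the plan says.** Mediation is stated in three places. Section I (Objectives) will "investigate the gut microbiota-mediated effect of whole wheat consumption". Section II.D (Summary) aims to uncover "the role of gut microbiota and their metabolites of whole wheat bread (WWB) components in mediating blood glucose excursions in prediabetes". Section VI.C.5 (Dietary Control) says the hypothesis under test is that whole wheat bread (WWB), "principally through its bioactive phytochemicals, improves glucose tolerance in a microbiota-mediated manner".

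The analyses are in section VI.B.3 (Power Calculation and Data Analysis):
- The primary comparison is of "within-subject changes (WWB endpoint vs. WB endpoint) between high-responders and low-responders". From 40 participants, 6-12 high-responders and 5-10 low-responders are expected.
- A mixed model has diet and time as fixed factors and participant as a random factor.
- Correlations are planned among features picked by their change in the high-responder group: "Spearman correlations will be calculated to define associations between microbes, inflammatory genes, metabolites that show significant changes in" that group.
- For microbes and response, the method is that "logistic regression will be fitted to each of the potential microbes or as a combination", with ROC analysis added. The purpose given for this step is one of association: "To test whether the changes in microbes after WWB intake associate with the biological response".

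Section VI.C.7 (Microbiota Composition) adds WWB versus white bread (WB) comparisons of total bacterial abundance, and multivariate community analyses.

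Section IV (Pitfalls and Alternatives) indicates that responders are to be defined on glycemic response, with HOMA-IR, endotoxin or inflammatory markers brought in if needed. Section III (Anticipated Results) says that consistent findings in a subset with larger glycemic changes would suggest, at least in part, a mechanism, namely "that the multi-facet health benefit of WWB consumption is gut microbiome-dependent".

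**The concern.** A mediation claim needs three things: an effect of diet on the microbial feature, an effect of the feature on glucose, and an estimate of how much of the diet effect passes along that path. Randomisation secures the first. Nothing in the plan estimates the third, and the second is approached only through a label derived mainly from the outcome. The high- and low-responder groups are not randomised, so anything that moves both microbes and glucose (adherence, transit time or other diet-sensitive physiology, for example) can separate them.

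At stake is what the report may say. If microbes differ between responder groups, the title, objective and hypothesis invite the conclusion that the benefit runs through the microbiota, and the listed analyses cannot carry that conclusion. Splitting participants into responder groups also sets aside the middle of the sample, although the crossover gives every completer a paired difference in both features and glucose.

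**Working it through.** **1. Claim against analysis.**

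| Link | Planned analysis | What it supports |
|---|---|---|
| Diet to glucose and other outcomes | Mixed model, diet as fixed factor | Randomised diet effect |
| Diet to microbiota | WWB v WB abundance and community comparisons | Randomised diet effect |
| Feature to feature | Spearman | Association; glucose is not among the named variables |
| Microbe to response | High/low contrast, logistic regression, ROC | Association with, or prediction of, a label |
| Diet to microbe to glucose | None | Nothing |

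No mediation model, mediator-outcome adjustment or sensitivity analysis is specified. Microbiota composition (VI.C.7) and the glucose tolerance test (VI.C.2) both fall on day 14 of each arm, so timing does not order mediator before outcome.

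**2. The plan's own figure.** Section VI.B.3 gives 80% power for a 1.6-fold difference in glucose AUC change, CV 0.5, alpha 0.05. Taking the effect as (1.6 - 1)/0.5 = 1.20 SD, two-sided normal approximation:

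power = Phi(d / sqrt(1/n1 + 1/n2) - 1.96)

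- 12 v 10: 1.20/0.428 = 2.80, and Phi(0.84) = 0.80.
- 6 v 5: 1.20/0.606 = 1.98, and Phi(0.02) = 0.51.

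The figure is met at the top of the stated range under this coding. It concerns the glucose contrast between responder groups and says nothing about a mediated effect, so the present point does not depend on it.

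**3. Can the responder analyses be positive without mediation?** Simulation, with assumptions chosen for illustration: 40 participants; the microbe change has no effect on the glucose change; a shared cause gives them correlation r; the 12 highest and 10 lowest glucose changes form the groups; 4,000 runs.

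| r from shared cause | High/low contrast significant | Mean ROC AUC | Spearman (all 40) significant |
|---|---|---|---|
| 0 | 5% | 0.50 | 5% |
| 0.2 | 19% | 0.64 | 22% |
| 0.3 | 37% | 0.70 | 42% |
| 0.5 | 83% | 0.82 | 89% |

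The analyses detect association correctly, but they cannot say where it comes from. The last column shows that using all participants does not cure this.

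**4. Cost of the responder label.** The groups total at most 12 + 10 = 22 and at least 6 + 5 = 11, so 18 to 29 of the 40 drop out of the contrast. The correlation detectable with 80% power in all 40 (Fisher z, two-sided 0.05, Pearson) is tanh((1.96 + 0.842)/sqrt(37)) = tanh(0.461) = 0.43. Simulating at a true r of 0.43, power is 0.81 using paired differences in all 40, 0.68 for 12 v 10, and 0.56 for 6 v 5, to within about 0.01.

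**The case against.** The strongest reply is that the protocol uses 'mediated' loosely. Section II.D, as it runs on, puts the aim in operational terms: compare the microbiota of those who improved with those who responded least, to see whether bacterial differences could explain the benefit in some people. Section II.B illustrates the idea with equol producers, and section III says the design serves precision nutrition. That is response depending on the microbes a person carries, and the responder, logistic and ROC analyses do address it as association. Section III says only that findings would suggest a mechanism, at least in part, and VI.B.3 speaks of association. All of this stands, and it limits the point to a mismatch between claim and analysis.

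Three stronger readings are tempting and are not supported:
- *Every planned analysis is a correlation or a prediction of responder status.* The mixed model and the WWB v WB microbiota comparisons are randomised diet contrasts. For the same reason the objective is not wholly unanswered: diet effects on the metabolomes, metabolic health and gut health can be tested.
- *Selecting features that changed in high-responders biases all the correlations upward.* In simulation with independent features selected at 0.05 in 12 high-responders, the false-positive rate between features was 5% within high-responders and 7% in all 40. With a true correlation of 0.3 and n = 12, selection lowered the mean Spearman estimate from 0.27 to 0.21-0.24. Inflation appeared when selected features were then related to glucose in all 40 (28% false positives), a step the plan does not state.
- *The protocol claims that responder findings would prove mediation.* Section III is conditional and hedged.

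An indirect effect computed as slope times mean feature difference also has a limit: it is near zero if WWB does not shift the feature on average, even when response depends entirely on which microbes a person carries.

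**Conclusion.** The point holds as a mismatch between the question and the analysis. The objective, aim and hypothesis are worded as mediation; the plan yields randomised diet effects and associations with a responder label, and no indirect effect. The hedges in sections III and VI.B.3 soften the expected interpretation but do not reach the wording of the title, objective or hypothesis.

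That no indirect effect is estimated follows from reading the plan and needs no assumption. The sizes do need assumptions. The 37% and 83% depend on an assumed shared-cause correlation of 0.3 or 0.5 and on groups of 12 v 10. The power comparison (0.81 against 0.68 and 0.56) assumes normal data, a true correlation of 0.43, responders taken as the extremes of the glucose change, and no dropout. The change should be made. It does not call the diet comparison into question.

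**What to change.** In VI.B.3, prespecify a short list of microbial features and metabolites. It should include the hypothesised wheat phytochemical metabolites as well as the SCFAs. For each, in all participants with both periods, fit

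dY = b0 + b1 x dM + b2 x (participant's mean M, centred) + error

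where dY is the WWB minus WB difference in glucose AUC, dM is the same difference in the feature, and mean M averages the feature over the two periods. The slope b1 is the association between the changes; b2 indicates whether the diet difference in glucose varies with the level of the feature a person carries. Do not pre-select features on significance in high-responders. The responder, logistic and ROC analyses can remain as secondary description.

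Optionally report the within-participant indirect effect, b1 x mean(dM), with a bootstrap interval, labelled exploratory and with its assumptions stated.

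Restrict conclusions to 'associated with' rather than 'mediated by', and align the wording of the objective and hypothesis with that.

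The cost is a small amount of extra analysis on samples and measurements already planned. The indirect-effect interval will be wide at n = 40 and still assumes no unmeasured mediator-outcome confounding, so this addition would not by itself establish mediation.
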